Introduction

Background and rationale {6a}

Long lasting insecticidal nets (LLINs) have contributed to the large reduction of malaria globally, particularly in sub-Saharan Africa in the last decade (1). However, malaria reduction is stalled or reversed in many malaria-endemic countries, including Tanzania. Reasons for this include increasing insecticide resistance of malaria vectors (2), low access to LLIN (3), LLINs not lasting up to three years so they wear out before the next mass distribution (4) and issues on compliance (5). Therefore, additional cost-effective and long-lasting vector control tools are required that will confer protection against insecticide resistant malaria vectors, and that protect every member of the household with minimal user compliance.

The vector control tool for evaluation in this trial is the dual active ingredient (dual AI) Insecticide-Treated Eave nets (ITENS) in combination with Insecticide Treated Window screens (ITWS) for house modification (Figure 1). These can protect everyone in the house by blocking mosquito entry and providing community protection by killing mosquitos that encounter them. The tool is coated with deltamethrin insecticide and piperonyl butoxide (PBO) synergist, both are found in insecticide treated nets that are already in use in the population to control pyrethroid resistant mosquitoes (6). A great advantage is they can be used with other AIs and can be used with AIs that cannot be used on bed nets because they do not come into daily contact with users. These nets are supplied on a roll and, as shown in a study in western Kenya, can be easily applied to houses using locally available tools in just 30 minutes per house (7). The pilot study in Kenya used pyrethroid only ITENS and ITWS among eighty households and showed a 75% reduction of vector densities in the houses using ITENS, ITWS and LLINs when compared to households using LLINs only (7).

This protocol described the activities that will be implemented in a trial designed to investigate the efficacy of ITENs with ITWS on malaria parasite prevalence measured by quantitative polymerase chain reaction (qPCR), and other secondary outcomes.

Figure 1. ITENs being installed. The net is provided on a roll and takes only 30 minutes to install, but lasts more than 4 years in Kenya.

[figure not shown]
Objectives {7}

The primary objective of the trial is to investigate the efficacy of ITENs with ITWS on malaria parasite prevalence among residents aged 6 months and above, measured by quantitative polymerase chain reaction (qPCR) shortly after long rainy season (June/July 2022), and after the short rainy season (January 2022) as a secondary outcome. Other secondary objectives are to estimate the effect of the interventions on clinical malaria cases, and density of malaria vectors and nuisance (*Culex quinquefasciatus*) mosquitoes after the i) short rainy season (January/February 2022) and ii) long rainy season (June/July 2022). The cost (fabric amount and time duration) of installing the intervention, perceived adverse effects after one month of installation, and physical durability and community acceptance of the tool after 6 months and 12 months installation, as well as chemical durability after 12 months of installation.

Trial design {8}

A household randomized superiority trial of households with ITENs and ITWS compared to those without them, among villages in Chalinze district located in Pwani region, Tanzania (Figure 2). Four hundred and fifty households will be randomly allocated equally into two arms, and will be surveyed twice in the subsequent year: short rainy season (January/February 2022) and long rainy season (June/July 2022). The surveys will assess the malaria prevalence of all participants using quantitative Polymerase Chain Reaction (qPCR) (8); clinical malaria cases defined by fever and malaria rapid diagnostic test (mRDT), SD Bioline; and the density of malaria vectors and nuisance mosquitoes will be measured using Centres for Disease Control (CDC) light traps (9).

In addition, a structured questionnaire will be used to obtain the estimated: i) time and material cost of installing the tool (feasibility) during installation, ii) perceived adverse effects after one month of installation, and iii) community acceptance of ITENs with ITWS. The physical durability of the intervention will be evaluated through physical inspection of the ITENs and ITWS for the continued presence and fabric integrity. Chemical durability will be assessed using samples of netting that will be evaluated for bioefficacy using laboratory reared populations of pyrethroid resistant *An. arabiensis*, *Culex quinquefasciatus*, *An. funestus* as well as pyrethroid susceptible *Aedes aegypti* mosquitoes, followed by chemical testing according to standard WHO guidelines and procedures (10). In addition, the perception, use and practice of the tool will be examined through Focus Group Discussions.

1 **Methods: Participants, interventions and outcomes**

2 **Study setting {9}**

3 The trial will be implemented in the villages of Pongwe, Madesa and Mazizi in Chalinze district
4 located in coastal Tanzania. The average rainfall is 1200 to 2100 mm per year and the average
5 temperature is approximately 28°C in the region. The region has two rainfall seasons yearly: the
6 long rainfall from March to May and short rainfall from November to December. The main
7 occupation for majority of the residents in villages of Chalinze is farming. The population of the
8 study area was 13,740 while the average household size in the district was 4.5 (11). The malaria
9 prevalence by PCR in the study area was more than 40% in the survey designed to assess
10 gametocyte in children of age 7 years old and above ([name]. *pers comm.*). More than sixty
11 percent of houses had window screens and thirteen percent had closed eaves in a study conducted
12 previously in the study area (11). An estimated 1800 people based on the average household size
13 and number of households will be tested for malaria at each survey, thus, nine hundred people per
14 arm will be screened for malaria.

15

16 **Eligibility criteria {10}**

17 Recruitment for the will be by household. To be eligible, residents must live in a house with strong
18 (intact) walls, having open eaves and unscreened windows. Residents of study houses who are
19 over the age of 6 months will be eligible for the follow up surveys.

20

21 **Eligibility criteria for individuals who will perform the interventions**

1 Carpenters required to install the ITENs and ITWS. Trained community technicians will be
2 recruited from the participating villages as they are most familiar with the house structures and
3 location. Technicians will i) collect information on the feasibility cost of installing ITENs and
4 ITWS, ii) collect mosquitoes with CDC light traps, iii) assess attrition, fabric integrity, bioefficacy,
5 chemical retainment, and iv) community practice and acceptance of ITENs and ITWS installed in
6 houses. Nurses/clinical officers or clinicians that will withdraw blood samples from household
7 members over 6 months for qPCR analysis and RDTs will also be recruited from the study villages.
8 The purpose of recruiting these individuals from the villages is to utilize their local knowledge and
9 community trust of these individuals as well as to contribute to building the capacity and economy
10 of the villages where the trial will be conducted.

11

12 **Who will take informed consent? {26a}**

13 Written informed consent in the local language, Kiswahili, will be voluntarily obtained by trained
14 field interviewers recruited from the villages. Informed consent will also be read aloud to non-
15 literates in Kiswahili in the presence of a witness and the participant will be asked to mark a thumb
16 impression on the form and the witness will be asked to sign to obtain acceptance of participation.
17 Consent for household participation will be sought from heads of households that are 18 years of
18 age and above. Additional written informed consent will be sought from individuals prior to
19 malaria testing. Participants under 18 years old will be recruited for malaria testing upon
20 combination of written informed consent from parent/guidance and assent from the child.

21

1 **Additional consent provisions for collection and use of participant data and biological**
2 **specimens {26b}**

3 Description of use of blood for malaria diagnostic using RDT and qPCR is explained in the written
4 informed consent. Samples will be used only for malaria screening and no samples will be stored
5 for further tests.

6

7 **Interventions**

8 **Explanation for the choice of comparators {6b}**

9 The control arm will consist of houses satisfying the eligibility criteria and that do not receive the
10 intervention. To estimate the additional protection of the intervention given the current malaria
11 control tool in use in the population, houses in the same location without the intervention is ideal.

12

13 **Intervention description {11a}**

14 **Intervention group**

15 The intervention is hardware insecticide treated netting that is used to cover the eaves (gaps
16 between the wall and roof) of houses and to screen windows. The insecticides coated in the ITENS
17 and ITWS are deltamethrin at 3g AI/kg, which corresponds to 144 mg/m² and PBO synergist at
18 10g/kg which corresponds to 480 mg/m², as used in the so-called dual-AI LLIN or “resistance
19 breaking” nets (6). The nets were manufactured by Moon Netting FZCO, United Arab Emirates.
20 The combinations of deltamethrin and PBO synergist has been shown to be efficacious against
21 pyrethroid resistant Anopheline mosquitoes and malaria (12). These nets are supplied on a roll and

1 attached to the wood around the roof, frame of the windows and on wood between walls using
2 staple guns and hammer. The nets will be used to cover all obvious mosquito entry points
3 including open eaves, windows and holes in house walls of between 10–25 cm diameter.

4

5 **Criteria for discontinuing or modifying allocated interventions {11b}**

6 Participants are free to withdraw from the study and they will be given the option to either keep
7 the intervention or uninstall the nets from the eaves and windows. If perceived unacceptable
8 adverse effects related to the intervention are reported by the participants, the intervention shall be
9 removed upon the request of the participants by the study team, as this is also discussed in the
10 Informed Consent form (Annex 1).

11

12 **Strategies to improve adherence to interventions {11c}**

13 ITENS and ITWS are hardwearing insecticide treated netting, thus minimal risk of non-adherence.
14 Houses allocated to the negative arm will have ITENS and IWS installed at the end of the trial.

15

16 **Relevant concomitant care permitted or prohibited during the trial {11d}**

17 At each survey, clinical officers/nurses/clinicians will withdraw blood samples from all
18 participants with an axillary temperature of 37.5 degrees or over for malaria parasites using a SD
19 Bioline Malaria Ag Pf/Pan rapid diagnostic test (RDT) for point of care as per Tanzania Ministry
20 of Health guidelines, and to establish clinical malaria cases. Any participant (s) that tests positive

1 using mRDT will be treated using free Artemether Lumefantrine (ALu). This drug is approved by
2 the national guideline for treatment of uncomplicated malaria (13).

3

4 **Provisions for post-trial care {30}**

5 ITENs & ITWS will be installed in houses randomly selected in the negative control arm at the
6 end of the trial to ensure that all groups have access to the intervention.

7

8 **Outcomes {12}**

9 **Primary outcome**

10 Prevalence of malaria measured by qPCR shortly after long rainy season (June/July, year 2022) in
11 households with ITENs and ITWS installed in comparison to those without.

12 **Secondary outcomes**

13 - Prevalence of malaria measured by qPCR shortly after the short rainy season (January/
14 February 2022) in households with ITENs and ITWS installed in comparison to those without.

15 - Prevalence of clinical malaria cases (defined by axillary temperature of 37.5 degrees or above
16 and positive mRDT) shortly after the short rainy season (January/February 2022) and long
17 rainy season (June/July 2022) in households with ITENs and ITWS installed in comparison to
18 those without.

19 - Density of malaria vectors and nuisance mosquitoes present in houses with ITENs and ITWS
20 installed in comparison to the houses without after the short (January/February 2022) and long
21 (June/July 2022) rainy season measured by CDC light trap.

- 1 - The amount of fabric and time cost of installing ITENs and ITWS per house.
- 2 - The percentage of adverse effects among technicians and houses with ITENs and ITWS after
3 one month of installation.
- 4 - The physical presence and numbers of holes visually observed in ITENs and ITWs after 6
5 months and 12 months of installation.
- 6 - The percentage knockdown and mortality at 24 hours of ITENs and ITWs after 12 months of
7 installation.
- 8 - The percentage chemical content of ITENs and ITWs after 12 months of installation.
- 9 - The percentage acceptance of ITENs and ITWS in the community using the structured
10 questionnaire.
- 11 - The behaviour, practice and use of ITENs and ITWS in the community from FGDs.

12

13

14

15

16

17

18

19

20

21

1 **Participant timeline {13}**

	STUDY PERIOD							
	Enrolment	Allocation	Post allocation					Closeout
TIMEPOINT	May	June, 2021	Aug 2021	Dec, 2021	Jan, 2022	June, 2022	July, 2022	Sept, 22
Eligibility screen/ baseline data	X							
Informed consent / Allocation	X							
Installation in the intervention arm		X						
Installation in the control arm								X
ASSESSMENTS								
Perceived adverse effect			X					
50 ul blood from members of above 6 months old					X	X		
Density of malaria vectors and Nuisance mosquitoes					X	X		
Feasibility Cost		X						
Longevity, fabric integrity, community acceptance and practice.				X		X		
Bioefficacy & Chemical retainment						X		

2

3

4 **Sample size {14}**

5 With 225 houses per arm was an assumed 4.5 residents per household (14), then if prevalence in
6 the control arm is 20% the study would have 90% power to detect a relative reduction of 30% to a
7 prevalence of 14% assuming a conservative between-house coefficient of variation of 0.5.

1

2 **Recruitment {15}**

3 Once permission from the District Medical Officer and village heads is obtained, meetings with
4 the village leaders will be convened to discuss the aim and procedures of the trial, and to select the
5 villages where houses that meet eligibility criteria can be found. Once villages are selected,
6 community sensitization will be conducted among all the selected villages to provide information
7 on the purpose of the study to the people, including the adverse consequences of vector-borne
8 diseases, the benefits and risks of using ITENS and ITWS, and caring for the intervention. This
9 will be followed by recruitment of the households through door-to-door process, facilitated by
10 community leaders as key informants to introduce field teams to households.

11

12 **Assignment of interventions: allocation**

13 **Sequence generation {16a}**

14 Household identification numbers stratified by sub-village will be provided to a statistician that
15 will not be in the field during the community enrolment. Simple randomization within blocks of
16 sub-villages to randomly allocate households between two arms will be conducted. Randomization
17 of all study households will be done simultaneously.

18

19 **Concealment mechanism {16b}**

20 This trial will not have continuous recruitment. All households will be recruited at the start of the
21 study and randomized simultaneously.

1

2 **Implementation {16c}**

3 After enrollment of all households by trained field workers, the trial statisticians will generate
4 allocation sequence and assign households to interventions through randomization stratified by
5 sub-village.

6

7 **Assignment of interventions: Blinding**

8 **Who will be blinded {17a}**

9 This is an open label trial because intervention can be visually observed.

10

11 **Procedure for unblinding if needed {17b}**

12 Not Applicable.

13

14 **Data collection and management**

15 **Plans for assessment and collection of outcomes {18a}**

16 Quantitative data such as malaria prevalence, clinical malaria cases, mosquito density, feasibility,
17 cost, adverse effects, attrition, integrity and use practice of the tool will be entered using Open
18 Data Kit (ODK) (15) installed on android tablet computers. Paper data forms will be available to
19 the field team for use in the eventuality of tablet computer failure. Data collected will be uploaded
20 to the IHI secure data repository for data analysis as per the requirement. Qualitative data will be

1 audio recorded (16). Interviews will be saved in an external hard-drive and locked in a secure file
2 cabinet. Mosquitoes will be collected using CDC light traps to measure the effect of the
3 intervention on the density of malaria vectors and nuisance mosquitoes (9). Blood samples will be
4 collected using New MiniCollect® K2EDTA Capillary Tube, manufactured by Greiner Bio-One,
5 Austria. The blood samples will be kept in cool box before they are transferred to the lab for qPCR
6 analysis. To confirm malaria cases, calibrated ear thermometer will be used to record body
7 temperature of those with positive mRDT. The study personnel, field workers/data collectors are
8 trained on correct data input methods to ensure data integrity.

9

10 **Plans to promote participant retention and complete follow-up {18b}**

11 Field interviewers recruited to support data collection will be from the study villages. Phases of
12 data collection will involve door to door surveys, with respective sub-village heads guiding field
13 interviewers to households, as participants are more likely to stay in the trial when familiar faces
14 are involved. Achieving complete follow-up in village settings may also be influenced by time of
15 data collection, as most of the study village residents are farmers and are more likely to be in their
16 farms throughout the daytime during cultivation and harvesting season, therefore follow up visits
17 for data collection will occur at a time when participants are available e.g. in the early morning or
18 evening. Data collectors will revisit absent households to ensure completeness of data collection.
19 However, in case of discontinuation by the participants, the information that will be recorded are
20 date, data collectors name, house code, GPS location and consent.

21

22 **Data management {19}**

1 Data collected using the ODK application installed on tablets will be uploaded onto the IHI secured
2 server and downloaded for analysis. Data collected using paper forms will be double entered into
3 a computer using double-key entry methods to facilitate cross-referencing and validation. The two
4 sets of entries will be compared, and any discrepancies found between the two databases will be
5 resolved by checking the data forms as per analysis plan. Audio recordings and notes taken during
6 the Focus Group Discussions will be stored securely. The data, both in hard copy and digital
7 format, collected will be kept for the purpose of analyses until consideration and clearance of the
8 final report.

9 Research records for all study participants including history and physical findings, laboratory data,
10 and results of consultations are to be maintained in a secure storage facility for 10 years or until
11 notified by grantee as per Tanzanian ethical guidelines. The grantee will be notified in writing and
12 acknowledgment must be received prior to destruction or relocation of research records. All raw
13 and cleaned data forms will be archived in the project office in a dedicated filing cabinet and all
14 data files will be retained on the IHI central data server in accordance with IHI and Tanzania
15 National guidelines.

16

17 **Confidentiality {27}**

18 All study related information will be stored securely at IHI. Data collectors are trained on
19 maintaining confidentiality of study participants' information. Households and participants will be
20 given unique identification numbers; thus, participant's study personal information will be
21 anonymized before analysis or if data will be shared based on data sharing agreement. Personal
22 information will only be shared based on written permission of the participant, for purposes of

1 independent monitoring among representatives of either government and regulatory authorities,
2 and/or site IRBs/ECs.

3

4 **Plans for collection, laboratory evaluation and storage of biological specimens for genetic or**
5 **molecular analysis in this trial/future use {33}**

6 Trained clinical officers/nurses/clinicians will screen for malaria parasites among all residents of
7 study households by withdrawal of no more than 500µl of blood for dry blood spots that will be
8 transferred to the laboratory at IHI, Kingani for detection of DNA of Plasmodium species (8) using
9 quantitative polymerase chain reaction (qPCR) analysis. Point of care diagnosis for febrile
10 individuals will be SD Bioline Malaria Ag Pf/Pan rapid diagnostic test (RDT) as per Tanzanian
11 guidelines (13).

12 Used RDT kits will be stored in a locked shipping container at IHI until the data is completed and
13 locked, then the samples will be destroyed on-site in the Clinical Trials facility Incinerator.

14

15 **Statistical methods**

16 **Statistical methods for primary and secondary outcomes {20a}**

17 The primary endpoint which is detection of malaria parasitemia through qPCR after the long rainy
18 season (June/July 2022) will be analysed using mixed effects binary logistic regression, with a
19 random effect for household to account for clustering. Analysis of secondary endpoints malaria
20 parasitemia will be tested using qPCR after the short rainy season (January/February 2022) as well

1 as clinical malaria cases and malaria prevalence shortly after the short rainy season and long rainy
2 will also be analysed following the same approach.

3 Negative binomial mixed effect model will be performed for mosquito density data, with random
4 effect for household.

5 The baseline characteristics collected during the survey, including age, sex, education, number of
6 participants, household size, occupation, sleeping spaces, nets per house, nature of houses (wall,
7 roof, and floor), community acceptance of LLINs (use rate and any side effects) and
8 socioeconomic quintiles will be presented by arm.

9 Principal component analysis (PCA) will be carried out to determine a combination of variables
10 for socioeconomic status to explain the overall observed variation and reduce the complexity of
11 the data, by calculating a weighted score for the socioeconomic status of each household of the
12 population and divided into five quintiles: lowest, low, middle, high and highest.

13 Proportion of the outcomes (attrition, fabric integrity and community acceptance) will be presented
14 in percentages.

15 Recorded information during the FGD will be transcribed and grouped into different themes based
16 on inductive thematic analysis of interview summaries. Reports will be illustrated with verbatim
17 quotes of themes and sub-themes identified.

18

19 **Interim analyses {21b}**

20 No interim analyses will be carried out.

21

1 **Methods for additional analyses (e.g. subgroup analyses) {20b}**

2 An analysis of the intervention effect within subgroups defined by age (under 5s, aged 5-15, and
3 aged 16 or over), socioeconomic status, gender, among others will be carried out on malaria
4 prevalence at both surveys using the same methods as for the primary endpoint.

5

6 **Methods in analysis to handle protocol non-adherence and any statistical methods to handle**
7 **missing data {20c}**

8 Minimal protocol non-adherence is expected because of the nature of the intervention, however
9 we will carry out an intention to treat in which households are analysed according to allocation
10 regardless of whether the intervention was adhered to. A secondary per protocol analysis which
11 excludes houses that removed the intervention will be carried out. At an individual level,
12 participants who report being away from home for more than a week during the fortnight preceding
13 testing will be excluded from the primary analysis but included in a secondary analysis. We expect
14 there to be minimal missing data on the primary endpoint, in which case complete case analysis
15 will be used. If there is more missing data than expected, a secondary analysis in which multiple
16 imputation is applied under the assumption of missing at random will be carried out.

17

18 **Plans to give access to the full protocol, participant level-data and statistical code {31c}**

19 Full protocol, statistical analysis plan, anonymized level-data and statistical code will be made
20 available on reasonable request.

21

1 **Oversight and monitoring**

2 **Composition of the coordinating centre and trial steering committee {5d}**

3 The Ifakara Health Institute is the trial sponsor and coordinating centre. Study investigators meet
4 weekly to review trial progress. A trial steering committee consisting of study investigators and
5 independent experts will meet after every study survey.

6

7 **Composition of the data monitoring committee, its role and reporting structure {21a}**

8 Although we don't anticipate any safety issues in this trial since the intervention is similar to LLINs
9 which are used extensively in malaria endemic regions a data monitoring committee has been
10 appointed. The committee is composed of a clinician, an entomologist and a statistician, is
11 independent of the trial sponsor and funder, and has no competing interests. The committee will
12 meet after the data from each survey have been collected. The committee will consider safety data
13 and data on trial endpoints and make recommendations on whether the trial should continue.

14

15 **Adverse event reporting and harms {22}**

16 The assessment of the risk to humans by the World Health Organization (WHO) (17) is that no
17 unacceptable exposures were found in maintenance and use of insecticides incorporated or coated
18 with deltamethrin and PBO synergist, and that washing or sleeping under them does not pose undue
19 risk to adults. Moreover, there is reduced contact with ITENs and ITWs. Nevertheless, participants
20 will be advised on possibilities of adverse effects. In case of serious adverse effect related to the

1 use of the study items, although not expected, affected participants will be provided with free
2 medical care.

3 An assessment of adverse effects will be made using a questionnaire given in Appendix 1, and will
4 be administered to carpenters and technicians as well as 50 randomly selected households in the
5 village at four weeks post-installation of ITENs and ITWS. The households will be selected by the
6 statistician using a simple random selection procedure blocked at sub-village level. The Principal
7 Investigator shall inform the Bagamoyo District Medical Officer and the IHI ethical review board
8 about possible reporting of adverse effects of use of ITENs and ITWS by the participants.

9

10 **Frequency and plans for auditing trial conduct {23}**

11 No trial audit is anticipated.

12

13 **Plans for communicating important protocol amendments to relevant parties (e.g. trial** 14 **participants, ethical committees) {25}**

15 Any protocol amendments and/or deviations will be fully justified and documented and agreed
16 upon by the sponsor study investigators, and village representatives. Application for such protocol
17 amendment will be written to the ethics committee and for clearance. If approval is attained from
18 the ethics committee, the changes to the protocol will be communicated to the participants via
19 village leaders and during study follow up.

20

21 **Dissemination plans {31a}**

1 Data will be disseminated by report to the sponsor, followed by peer-reviewed publication targeted
2 towards consumers, scientists and policy-makers. We will publish the results and data sets in open-
3 access, indexed, peer-reviewed journals, making the findings and the anonymized data publicly
4 available to all stakeholders. Data obtained from the study will be presented at international
5 conferences and stakeholder meetings including the National Malaria Control Program. At the end
6 of the project a meeting will be held to update the local community and the District Medical Officer
7 (DMO), to present findings and answer any questions arising.

8

9 **Discussion**

10 For malaria control, demonstrating the effectiveness of ITENs and ITWS would bring many
11 benefits. ITENs and ITWS have the potential to be long lasting, cost-effective and protect
12 everybody in the household at all times when they are indoors. The interventions can be fitted to
13 any house style, unlike traditional house screening that is costly and better suited to improved
14 housing designs. Unlike LLINs, they require no compliance from the user. Data from a pilot study
15 in Kenya indicate that ITENs/ ITWS are far more cost-effective than LLINs, costing USD 1 - 1.75
16 less per household per year (assuming 3 nets and 6 people per household) due to lower material
17 costs and improved longevity; and the saving is even greater compared to indoor residual spraying.
18 In a separate study, the efficacy of ITENs and ITWS in the Semi Field System (SFS) setting against
19 dengue vectors will be examined; and it is likely that ITENs and ITWS could work against other
20 vector borne diseases such as filariasis. It is desirable as a means of preventing nuisance mosquito
21 bites, which will likely improve uptake of the intervention. ITENs and ITWS are good candidates
22 for deployment of new insecticides as they are not washed or in close contact with users and the
23 fast knockdown characteristic of pyrethroids may not be required. This may offer great advantages

1 in insecticide resistance management, as different insecticides to those applied to LLINs can be
2 used in further iterations of the tool once proof of efficacy. There may also be an economic boost
3 to low-income countries that use ITENS and ITWS. Approximately 85% of the jobs associated
4 with LLIN production are in cutting and sewing activities (fabric to finished LLIN). Since the
5 material for ITENS and ITWS is sent on rolls and installation occurs at the site of implementation,
6 there is a transfer of employment from the manufacturing site to the malaria endemic country.

7 A limitation of this trial is that randomization is at the household level rather than the village level.
8 This means the trial will only capture direct effects of the intervention and not capture indirect

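### The 90% power assumes 4.5 tested residents per house (about 1,012 per arm), but Study setting plans 900 per arm, where power is about 87%; and 450 × 4.5 is 2,025, not 1,800

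*Protocol*

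**What the plan says.** Trial design {8} fixes the number of randomised units: "Four hundred and fifty households will be randomly allocated equally into two arms", so 225 houses per arm.

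Sample size {14} starts from "With 225 houses per arm was an assumed 4.5 residents per household". For a control prevalence of 20% it says that "the study would have 90% power to detect a relative reduction of 30% to a" "prevalence of 14% assuming a conservative between-house coefficient of variation of 0.5". It states neither alpha nor sidedness, and no allowance for residents who are not tested or not analysed.

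Study setting {9} also gives 4.5 as the district's average household size. It then projects the number tested: "An estimated 1800 people based on the average household size" "and number of households will be tested for malaria at each survey, thus, nine hundred people per" arm. It names household size and number of households as the only basis for that projection.

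The section on non-adherence and missing data {20c} removes from the primary analysis people who were away for more than a week in the two weeks before testing. Eligibility criteria {10} limit the surveys to residents over 6 months of age.

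**The concern.** Both sections claim to rest on household size and house count, yet they give different numbers for the population in which the primary outcome is measured: about 1,012 per arm in {14} and 900 per arm in {9}. They cannot both be right.

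The gap matters because the power calculation has no margin. It reaches 90% only if every one of the 4.5 residents per house contributes a result. If 900 per arm is the realistic yield, the stated power is too high, and a null result would be read against a figure that the design does not support. If 4.5 per house is meant, the projected number tested is a wrong product. Either way, one of the two printed figures needs correcting.

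**Working it through.** **Inputs**
- Houses per arm: c = 225 ({8}, {14}).
- Control and intervention prevalence: p0 = 0.20, p1 = 0.14 ({14}).
- Between-house coefficient of variation: k = 0.5 ({14}).
- Residents per house: m = 4.5 ({14}), or m = 900/225 = 4.0 from the number tested in {9}.
- Alpha: not stated. Two-sided 5% is assumed because it reproduces the stated 90%; one-sided 5% would give 94.4% at m = 4.5.

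**Head count**
- 450 × 4.5 = 2,025 in total; 225 × 4.5 = 1,012.5 per arm.
- 1,800/450 = 4.0 people per house. Equivalently, 1,800/4.5 = 400 houses.

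**Formula** (comparison of two proportions in a cluster-randomised trial, with a between-cluster coefficient of variation)

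V = p0(1−p0)/m + p1(1−p1)/m + k²(p0² + p1²)

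Houses per arm for 90% power: c = (1.96 + 1.2816)² × V/(p0−p1)², plus 1 in the version with a small-sample correction.

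Power = Φ(√[c(p0−p1)²/V] − 1.96), with c−1 in place of c in the corrected version.

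Here (1.96 + 1.2816)² = 10.507 and (p0−p1)² = 0.0036.

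**Reproducing the stated 90% (m = 4.5)**
- V = 0.16/4.5 + 0.1204/4.5 + 0.25 × (0.04 + 0.0196) = 0.03556 + 0.02676 + 0.01490 = 0.07721.
- Houses needed: 10.507 × 0.07721/0.0036 = 225.4 (226.4 with the correction).
- Power at 225 houses: Φ(3.239 − 1.96) = 90.0%, or 89.8% with the correction.

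This is evidently the calculation behind {14}.

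**At the stated 900 per arm (m = 4.0)**
- V = 0.0400 + 0.0301 + 0.0149 = 0.0850.
- Power at 225 houses: Φ(3.087 − 1.96) = 87.0%, or 86.9% with the correction.
- Houses needed for 90%: 10.507 × 0.0850/0.0036 = 248.1 (249.1 with the correction).
- With 225 houses, 90% power holds only for a fall to about 13.7%, a relative reduction of about 31.4%.

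**Sensitivity to the method and to the reading of 900**

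| Version | 4.5 per house | 4.0 per house |
|---|---|---|
| Coefficient-of-variation formula | 89.8–90.0% | 86.9–87.0% |
| Design effect, control-arm ICC 0.0625 | 90.3–90.4% | 87.6–87.7% |
| Design effect, average ICC 0.052 | 91.2–91.3% | 88.4–88.6% |
| Formula with reduced within-house variance | 91.0–91.2% | 88.3–88.4% |

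The loss is about 3 points in every row, and every value at 4.0 is below 90%. If 900 is read instead as 200 houses of 4.5, power is 86.1–86.3%.

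**Further losses (assumed; the protocol gives no rates)**
- 10% of the 900 not analysed (3.6 per house): about 84%.
- 20% not analysed (3.2 per house): about 80%.

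**The case against.** The strongest defence is that {14} is correct on its own terms. It is conditional on 4.5 residents per house and it reproduces. On that view the error is one wrong product in a descriptive paragraph that calls its figure an estimate, and if 2,025 is the intended number the power stands. This is fair as far as it goes: the protocol does not say which number is meant, so the 87% is conditional on the 900 per arm in {9}.

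The 3 points are also small beside the uncertainty in the other inputs. At 4.0 per house and a 30% reduction, power returns to 90% if control prevalence is about 22.2%, and is about 93% at 25% and 99% at 40%. It also returns to 90% at 20% prevalence if the coefficient of variation is about 0.33. Study setting {9} cites local PCR prevalence above 40%, though in a survey of people aged 7 and over, and {14} calls its 0.5 conservative. All this limits the practical consequence. It does not rescue the printed claim, which is made at 20% and 0.5, and it does not reconcile 1,800 with 2,025.

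Finally, 1,800 is about 11% below 2,025 and might already contain an unstated allowance for infants, absence or refusal. In that case the 84% and 80% scenarios would partly count the same losses twice. The protocol also plans visits at convenient hours and revisits ({18b}), and expects little missing data ({20c}). But {9} mentions no allowance, and if one was intended, 4.0 per house is the realistic yield and {14} overstates the power.

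**Conclusion.** The concern holds. Study setting {9} and Sample size {14} contradict each other on how many people will be tested, and 1,800 does not follow from the household size and house count given as its basis. The 90% belongs to about 1,012 tested per arm. At the protocol's own 900 per arm it is about 87%, or 87.6–88.6% under the alternative variance formulas. These figures assume two-sided 5% and keep the protocol's 20%, 14% and 0.5. The shortfall is modest, about 3 points. Because 90% is reached with no reserve, any resident not tested, or excluded under {20c}, lowers it further; how far is unknown, and the 84% and 80% figures are illustrations only.

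**What to change.** Make the two sections agree on the number tested per house:

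- If 1,800 is the realistic number, restate {14} as 225 houses per arm with 4.0 tested residents per house (900 per arm). Power is then 87% for 20% versus 14%, or 90% for a fall to about 13.7%.
- If 4.5 per house is intended, correct {9} to 2,025 in total, about 1,012 per arm.

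In either case, state alpha and sidedness, and quote power for the number expected in the primary analysis after the age limit, absence, refusal and the {20c} exclusion, with the assumed loss written down.

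The cost is a text correction. Household recruitment and allocation are complete, and no further households are needed. Under the first option the stated power becomes about 3 points less favourable, before any allowance for further losses.
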